3.4 Safety Endpoints

All adverse events related to the use of the μ Cor will be used to assess safety during the study.

4 Study Subject

4.1 Inclusion Criteria

The following criteria will be used to include subjects in the study: An acute heart failure event requiring medical management is defined in section 6.1.3.

- 4.1.1 Subjects being discharged from the hospital for acute decompensated heart failure either HFrEF (systolic) or HFpEF (diastolic) OR subjects who have been discharged from the hospital with either HFrEF (systolic) or HFpEF (diastolic) within the previous 10 days.
- 4.1.2 Subjects who have had an acute heart failure event requiring medical management in the previous 6 months.
- 4.1.3 Subjects 21 years of age or older on the day of screening.

4.2 Exclusion Criteria

The following criteria will be used to exclude subjects from the study:

- 4.2.1 Subjects who are wearing the wearable cardioverter defibrillator (WCD)

- 4.2.2 Subjects not expected to survive one year from enrollment from non-cardiac disease.
- 4.2.3 Subjects with skin allergy or sensitivity to medical adhesives.
- 4.2.4 Subjects anticipated to start dialysis within 90 days.
- 4.2.5 Subjects currently implanted with an S-ICD system.
- 4.2.6 Subjects who received a percutaneous coronary intervention (PCI) less than 24 hours after onset of heart failure related symptoms during index hospitalization.
- 4.2.7 Subjects who are unable to participate in all follow up visits.
- 4.2.8 Subjects participating in any other research at time of enrollment.
- 4.2.9 Subjects currently implanted with an LVAD.
- 4.2.10 Subjects with self-reported pregnancy.

5 Study Enrollment Plan

5.1 Enrollment Strategy

Patient enrollment strategies may be targeted at both the investigator and the patient as a way to engage all interested parties and provide information materials for the study. Strategies may include patient and/or investigator focus groups, educational lectures, web sites, flyers, or brochures to assist in the recruitment and screening process, if needed. Any patient facing materials will be submitted for approval to the IRB.

5.2 Study Size

A total of 500 subjects.

5.3 Enrollment Period

The anticipated total enrollment period for this study is 1 year, with a total anticipated study period would be 2.5 years.

5.4 Early Withdrawal of Subjects

5.4.1 When and How to Withdraw Subjects

All patients enrolled into the study can withdraw at any time regardless of the reason for withdrawal. Patients may withdraw consent for use of data and exit the study at any time without prejudice to further treatment.

5.4.2 Data Collection and Follow-up for Withdrawn Subjects

Reason for subject withdrawal from the study, if known, will be documented and all study data will be retained for data analysis. All possible attempts should be made to obtain follow up data at the end of study without contacting the subject. Only in the case of specific withdrawal of consent of use of data will the subject's data be deleted from the database (if possible).

6 Study Procedures

6.1 Subject Recruitment and Screening

6.1.1 Subject recruitment

Subjects will be identified from chart review. Subjects may be recruited in both inpatient and outpatient settings. The investigator will discuss the details of the clinical study including benefits and risks of participating in the study prior to enrollment.

6.1.2 Subject screening

Subject chart review will take place based on the inclusion/exclusion criteria.

6.1.3 Screening definitions

An acute heart failure event requiring medical management is defined as a hospitalization, emergency room visit, observation unit visit, or unplanned clinic visit where medical management or treatment for HF related pulmonary congestion is administered.

6.2 Scheduled Visits and Phone Calls

The scheduled visits are summarized in Table I and include the initial visit along with visits at day 30, 60, and 90. There will also be weekly phone calls to the patient. No monthly visits or weekly phone calls will occur if the subject has stopped wear. The phone calls will be conducted within no more than 2 days before or after the scheduled date. The scheduled visits will be conducted within no more than 5 days before or after the scheduled date. During the optional extended 90 day wear period, scheduled clinic visits and weekly phone calls will continue to take place following the procedures in Visits 2-4 with the exception of 6.2.4.6 (asking again for additional wear). Chart review and a follow up phone call will take place at 6 months and 1 year post enrollment.

6.2.1 Visit 1: Screening, enrollment and start (To occur during hospital discharge for decompensated heart failure or during a clinic visit in an out-patient setting no more than 10 days post hospital discharge).

6.2.1.1 All subjects will complete the Kansas City HF and study specific questionnaire.

6.2.1.2 A chart review will be used to evaluate patients for enrollment. A screening log will be maintained.

- 6.2.1.3 Patients meeting the initial Inclusion/Exclusion criteria will be approached for consenting.
- 6.2.1.4 The initial clinical and demographic data will be recorded in every subject. These may be done by chart review and will include:
- 6.2.1.5 Demographic characteristics, including gender, age, height and weight will be recorded.
- 6.2.1.6 Medical history will be recorded, including comorbidities, heart disease and physical disability.
- 6.2.1.7 Medical therapy for heart failure will be recorded for all subjects.
- 6.2.1.8 LVEF measurement within the past 30 days will be recorded if available. If a previous LVEF is not available, one will be obtained within 30 days of enrollment.
- 6.2.1.9 Subjects will be given a physical assessment.
- 6.2.1.10 Subjects will be assigned to wear the patch at either the front or side location (alternating 1:1)
- 6.2.1.11 Subjects will be fitted with μ Cor at hospital discharge or departure from clinic.
- 6.2.1.12 Device fitting will follow current Instructions for Use (IFU) procedures.
- 6.2.1.13 The date and time when μ Cor wear began will be recorded.
- 6.2.1.14 A clinic visit appointment will be scheduled to coincide with the end of the first 30 days of μ Cor wear.
- 6.2.1.15 The subject's weight will be obtained.
- 6.2.1.16 The subject's previous 90 day hospital admission rate will be determined through chart review.

6.2.2 Visit 2: μ Cor Wear Day 30.

- 6.2.2.1 All subjects will complete the Kansas City HF and study specific questionnaire.
- 6.2.2.2 An in-center appointment will be scheduled to coincide with the end of 60 days of μ Cor wear.
- 6.2.2.3 All subjects will be asked about the following events since their last visit:
 - Any medication changes
 - Any physician visits, both planned and unplanned
 - Any hospitalization, including heart failure hospitalization
 - Any emergency room visits
 - Any symptoms, including syncope, dyspnea, palpitations and chest pain

6.2.2.4 A weight measurement will be obtained.

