2.2 Secondary Objective(s)

The specific secondary objectives that will be evaluated during the entire study include:

- 2.2.1 To identify the rate of occurrence of VT/VF and arrhythmic death in heart failure patients based on left ventricular ejection fractions (LVEF).
- 2.2.2 To identify correlations between μ Cor measurements (physiologic variables including thoracic impedance, cardiac rhythm, respiration rate,) and patient reported symptoms.
- 2.2.3 To identify the hospital admission rate of patients during the study period.
- 2.2.4 To identify the hospital admission rate of patients in the previous 90 days before enrollment into the study.

- 2.2.5 To define the mortality rate, cause of death, and health care utilization among patients six months and one year after enrollment into the study.

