3.1 General Design

3.1.1 Study Description

Subjects meeting the inclusion/exclusion criteria will wear μ Cor for up to 90 days from the day of fitting. 500 total patients will be enrolled. There will be an interim analysis when the 200th subject has finished the study to assess for distribution of patients with reduced and preserved LVEF. The first 200 subjects enrolled in the US will exclusively wear the device in the side position. The subsequent subjects in the US will follow an alternating pattern of front position and side position placement.

Subjects will be fitted with μ Cor during discharge of a heart failure related hospitalization or within a clinic visit that has occurred within 10 days of a heart failure related hospitalization. The μ Cor fitting will mark day 0 of the study. An LVEF measurement will be recorded during enrollment or within 30 days post enrollment if an LVEF measurement has not been recorded within 30 days prior to enrollment. An investigator assessment will be performed during all clinic visits. The assessment template is shown in Appendix A.

Subjects will be given a diary at enrollment that will ask them to rate their degree of specific symptoms of heart failure such as shortness of breath and fatigue as well as mark any heart failure related clinical events or medication changes that have occurred since the last entry. The subject diary is shown in Appendix A.

Study follow up visits will occur at day 30, day 60, and day 90. There will be no follow up visit if the subject has stopped wearing the device. During follow up visits the subjects will be asked about any heart failure related clinical events or change in symptoms that have occurred since the last follow up. The subject will receive a study based weekly phone call asking the subject about any recent heart failure related clinical events or change in heart failure symptoms. During the weekly phone call the subject will be reminded to fill out the daily diary. No phone calls will be given on the week where there is a study follow up visit. There will be no follow up visit if the subject has stopped wearing the device. In case of adverse skin reaction to the μ Cor adhesive and/or electrodes, on the discretion of physician, subjects may discontinue wearing the device for

up to 48 hours. In the event the subject has stopped wearing the device completely, follow up phone calls will continue to be conducted per protocol in order to capture clinical information.

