3.3 Secondary Study Endpoints

The various secondary endpoints that will be evaluated during the entire study include:

- 3.3.1 Establishment of rate of occurrence of VT/VF episodes and arrhythmic death in patients.
- 3.3.2 Correlation between μ Cor measurements and patient reported symptoms
- 3.3.3 Frequency, timing, and severity of patient reported symptoms
- 3.3.4 Hospital readmission rate during the study period
- 3.3.5 Hospital readmission rate during previous 90 days prior to enrollment in study.
- 3.3.6 Cost-effectiveness data that supports a benefit in quality adjusted life years (QALY)
- 3.3.7 Mortality, heart failure related events, and health care utilization data at six months and one year post enrollment

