6.6 Weekly Phone Calls

There will be weekly phone calls to the subject to monitor changes in the health status of the subject. These calls will be performed by the site. The calls will reiterate the importance of completing the daily subject diary and document any health care usage by the subject. The calls will also document any heart failure related clinical events reported by the subject. No phone calls will occur if the subject has stopped wear.

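### The prior-90-day admission rate rests on chart review while on-study admissions are also reported by subjects, so the prior rate tends to be under-ascertained and the two rates are not on the same footing

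*Combined protocol and SAP*

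**What the plan says.** Section 2.2 sets two adjacent secondary objectives. Objective 2.2.3 is "To identify the hospital admission rate of patients during the study period". Objective 2.2.4 is "To identify the hospital admission rate of patients in the previous 90 days before enrollment into the study". Section 3.3 repeats them as endpoints 3.3.4 and 3.3.5, the latter worded as "Hospital readmission rate during previous 90 days prior to enrollment in study".

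The prior-period rate has one named source. Under Visit 1, section 6.2.1.16 says the "previous 90 day hospital admission rate will be determined through chart review".

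On-study admissions have several:

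- At Visits 2 and 3 (6.2.2.3, 6.2.3.3), "All subjects will be asked about the following events since their last visit", and the list includes "Any hospitalization, including heart failure hospitalization". Visit 4 (6.2.4.3) carries the same item without the look-back phrase.
- The weekly calls in section 6.6 are to "document any health care usage by the subject".
- The diary (3.1.1) asks subjects to "mark any heart failure related clinical events or medication changes that have occurred since the last entry", and the sample page in Appendix A has a daily hospitalization column.
- Section 6.4 adds a call at 6 months and at 1 year about health care use since the end of wear, each with a chart review.

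Section 8.4 plans descriptive statistics for the secondary endpoints. No ratio, difference or test of the two admission rates is specified.

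**The concern.** The same quantity is measured in two ways. Before enrollment it is what a chart review finds. On study it is what records show plus what the subject reports, repeatedly and at short intervals. Chart review finds an admission elsewhere only if that admission reached the chart being read. A subject who is asked can report it wherever it took place.

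Two things are at stake. First, the prior rate is an endpoint in its own right, and incomplete capture lowers it whether or not it is compared with anything. Second, the two rates sit side by side in the objectives, and a 90-day look-back next to a planned 90-day wear period invites a reader to compare them. Part of any difference would then reflect how admissions were found rather than how many occurred.

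**Working it through.** The documents state no admission rate, capture fraction or precision for these endpoints, so there is no figure to reproduce. The check sets the sources side by side and then illustrates the possible size with assumed values.

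**Sources, by period**

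| Source | 90 days before enrollment | On study |
|---|---|---|
| Chart review | Yes (6.2.1.16) | Yes, at 6 months and 1 year (6.4) |
| Direct question at a visit | None named at Visit 1 | Visits 2 to 4 |
| Weekly call | Not applicable | Yes (6.6) |
| Diary | Not applicable | Yes (3.1.1, Appendix A) |
| Later call | Not applicable | Yes (6.4) |

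Every source that rests on subject report falls in the right-hand column.

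**Illustration**

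Assumed inputs, none of them in the documents:

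- m: share of prior admissions that chart review misses, taken as 0.10, 0.20 and 0.30. Chart capture is c = 1 − m.
- f: share of on-study time with subject contact, taken as 1.0 and 0.7.
- Capture is complete under contact and falls to c otherwise.
- True rates are equal in the two periods, subject-reported admissions count in the on-study rate, and the index stay is not counted.

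Apparent on-study/prior ratio = [f + (1 − f)c] / c.

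| m | c | f = 1.0 | f = 0.7 |
|---|---|---|---|
| 0.10 | 0.90 | 1/0.90 = 1.11 | (0.70 + 0.27)/0.90 = 0.97/0.90 = 1.08 |
| 0.20 | 0.80 | 1/0.80 = 1.25 | (0.70 + 0.24)/0.80 = 0.94/0.80 = 1.18 |
| 0.30 | 0.70 | 1/0.70 = 1.43 | (0.70 + 0.21)/0.70 = 0.91/0.70 = 1.30 |

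The f = 1.0 column is the upper case. If on-study capture fell to 90% and chart review also captured 90%, the ratio would be 0.90/0.90 = 1.00.

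**If the index stay is counted in the prior window**

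Entry requires a discharge at enrollment or within the 10 days before it (4.1.1), so the site knows of that stay and cannot miss it. Let x be the other prior admissions per subject (assumed). Missing a share m of those inflates the ratio, relative to complete capture, by (1 + x) / (1 + x(1 − m)). At m = 0.30:

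- x = 0.3: 1.30/1.21 = 1.07
- x = 0.5: 1.50/1.35 = 1.11
- x = 1.0: 2.00/1.70 = 1.18

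Counting the index stay also adds about one admission per subject to the prior period only, which pushes the ratio the other way. For example, with 0.3 other admissions per subject before enrollment, 0.3 on study and chart capture of 0.70, the ratio is 0.3/1.21 = 0.25.

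**The case against.** The strongest reply has four parts.

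*On-study capture is incomplete too.* Visits stop when wear stops (3.1.1, 6.2). Sections 6.2 and 6.6 stop the weekly calls as well, although 3.1.1 says they continue. Withdrawn subjects are followed without contact (5.4.2), and missed calls, missed visits, unavailable records and loss to follow-up are expected (8.6.1). This stands. A reader might infer that admissions outside the chart are missed only before enrollment, and the documents do not support that. The calls in 6.4 narrow the on-study gap but depend on long recall. The imbalance shrinks, and it would disappear if on-study capture fell to the chart-only level.

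*The chart may be wider, and Visit 1 may ask more, than it seems.* A reader might take chart review to mean the enrolling hospital's own chart, but 6.2.1.16 sets no such limit and 12.2.1 lists hospital records and office charts among source documents. A reader might also infer that the subject is asked nothing at Visit 1. That cannot be shown: Visit 1 includes a study specific questionnaire whose content is not given (6.2.1.1), and Table 1 marks HF event documentation at that visit. Neither is named as a source for this rate, however, and HF event documentation would not by its title cover admissions for other causes, to which 2.2.4 also extends.

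*No comparison is planned.* This is true, and a misleading comparison is therefore a reader's risk rather than a flaw in a planned inference. It does not answer the under-capture of the prior rate itself.

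*The index stay could outweigh everything else.* This also stands. It removes any claim about net direction, but it does not supply the missing source.

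**Conclusion.** The point holds as a difference in ascertainment. As written, the prior-90-day rate has chart review as its only named source, while the on-study rate also draws on repeated subject report. Admissions absent from the chart are more likely to be missed before enrollment, so the prior rate tends to be too low.

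The size is not known. Ratios of 1.11, 1.25 and 1.43 are upper values. They rest on assumed missed shares of 10%, 20% and 30%, complete on-study capture, and an index stay left out of the count. With contact for 70% of on-study time they become about 1.08, 1.18 and 1.30. The inflation is smaller still if the index stay is counted.

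A reader might go on to infer that the trial would show a spurious rise in admissions or hide a real fall. The documents do not support that: no comparison is prespecified, they do not say whether the index stay counts or which source defines the on-study rate, and the index stay could push the contrast the other way. This is a modest, cheaply corrected weakness in a descriptive secondary endpoint. It does not touch the primary objective.

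**What to change.** Change 6.2.1.16 so that the rate is *determined by chart review and by asking the subject at Visit 1 about admissions to any hospital in the previous 90 days*. The item from Visits 2 and 3 cannot be copied unchanged, because its look-back runs from the previous visit.

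Record the source of each admission (chart, subject or both) in both periods. A chart-only rate can then be shown for each period as a like-for-like check beside the all-source rate. For that check, 6.4 should state that the later chart review reaches back to enrollment, since it does not say which window the review covers.

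In the same revision, state whether the index stay counts in the prior rate, define the on-study window and its person-time denominator, and reconcile 3.1.1 with 6.2 and 6.6 on calls after wear stops.

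The cost is one question and one source field. The downside is error in 90-day recall, which the source field makes visible.

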6.2.2.5 Subjects will be given a physical assessment

6.2.3 Visit 3: μ Cor Wear Day 60.

6.2.3.1 All subjects will complete the Kansas City HF and study specific questionnaire.

6.2.3.2 An in-center appointment will be scheduled to coincide with the end of 90 days of μ Cor wear.

6.2.3.3 All subjects will be asked about the following events since their last visit:

- Any medication changes
- Any physician visits, both planned and unplanned
- Any hospitalization, including heart failure hospitalization
- Any emergency room visits
- Any symptoms, including syncope, dyspnea, palpitations and chest pain

6.2.3.4 A weight measurement will be obtained.

6.2.3.5 Subjects will be given a physical assessment.

6.2.4 Visit 4: μ Cor Wear Day 90.

6.2.4.1 μ Cor use will be discontinued unless patient enters optional additional wear period.

6.2.4.2 All subjects will complete the Kansas City HF and study specific questionnaire.

6.2.4.3 All subjects will be asked about the following clinically actionable events:

- Any medication changes
- Any physician visits, both planned and unplanned
- Any hospitalization, including heart failure hospitalization
- Any emergency room visits
- Any symptoms, including syncope, dyspnea, palpitations and chest pain

6.2.4.4 A weight measurement will be obtained.

6.2.4.5 Subjects will be given a physical assessment

6.2.4.6 Subjects will be asked if they would like to continue wear for an additional 90 days. If the subject had experienced a heart failure related clinical event within the previous 90 days, the subject will also be given the option to continue wear for 30 days following the most recent heart failure event.

6.3 *Unscheduled Visits*

NA

6.4 Long-term Clinical Outcome Assessment

The subject will receive a follow up phone call 6 months and 1 year from the enrollment date to assess for mortality status, heart failure related clinical events that have occurred since the end of μ Cor wear, and any health care utilization that has occurred since the end of μ Cor wear. A chart review will be performed during both of these calls as well. Subjects will answer mailed heart failure questionnaires and mail the questionnaires back to the site.

6.5 Study Procedures Flowchart (or Table)

Summary of the activities and procedures to be followed at each visit is as described below (Table 1).

	Visit 1	Visit 2	Visit 3	Visit 4	6 Months	1 Year
Eligibility Screening	X					
Consent	X					
Enrollment	X					
Physical Assessment	X	X	X	X		
μ Cor Setup	X					
EF Documentation*	X					
HF Event Documentation	X	X	X	X	X	X
Weight Documentation	X	X	X	X	X	X
HF Questionnaires	X	X	X	X	X	X

Table 1: Visit Procedure List (*All EF measurements will be documented if clinically indicated)

6.6 Weekly Phone Calls

There will be weekly phone calls to the subject to monitor changes in the health status of the subject. These calls will be performed by the site. The calls will reiterate the importance of completing the daily subject diary and document any health care usage by the subject. The calls will also document any heart failure related clinical events reported by the subject. No phone calls will occur if the subject has stopped wear.

6.7 Blinding and Unblinding of Study

During the study, physicians and subjects will be blinded to all μ Cor data. If the sponsor observes a potentially life threatening arrhythmia, the site will be notified.

7 Study Device Management

The μ Cor device log will be managed by the sponsor. The sites will keep a device log of all available μ Cor devices and make necessary requests to the sponsor when inventory is low. The study site will collect the device when the patient has ended wear. All used and unused devices will be returned to the sponsor when the study is completed. The investigator will be responsible for subject device accountability.

